- The treatment duration will be up to 52 weeks.

- The visit frequency will include visits at weeks 1, 5, 13, 26, 39, 52, and 56.

Treatment of interest

The treatment of interest is LTP001 [REDACTED] mg daily on top of allowed standard of care treatment for PAH. The dose of the allowed concomitant medication should remain stable during the trial.

Number of Participants:

The study population is comprised of male and female adults with PAH. A total of approximately 40 participants are planned to complete the parent study CLTP001A12201 and meet the study entry criteria for this open label extension study.

Key Inclusion criteria:

- Written informed consent must be obtained before any assessment is performed.
- Participant is currently completing the Novartis-sponsored study CLTP001A12201 in PAH and completed key efficacy and safety procedures up to the end of treatment of the parent study, without meeting discontinuation criteria in the parent study.
- Willingness and ability to comply with scheduled visits, treatment plans and any other study procedures.
- In the opinion of the Investigator the participant would benefit from LTP001 treatment.

Key Exclusion criteria:

- History of hypersensitivity to the study treatment.
- Required or planned transplant or heart/lung surgery.
- Acute or chronic impairment (other than dyspnea), which would limit the ability to comply with study requirements, including interference with physical activity or execution of study procedures such as 6MWT (e.g., angina pectoris, claudication, musculoskeletal disorder, need for walking aids).
- Permanent discontinuation of Novartis drug in the parent study due to toxicity or disease progression, non-compliance to study procedures, withdrawal of consent or any other reason.

Treatment Groups:

Active treatment: LTP001 administered as [REDACTED] mg once daily CCI [REDACTED] (CCI [REDACTED]). Investigational study treatment dose adjustments and/or interruptions are not permitted.

Data Monitoring/Other Committee:

Yes; the DMC instituted for the parent study will also receive data from this extension study (see [Section 10.1.4 Committees Structure](#)).

Key words:

Pulmonary arterial hypertension, pulmonary vascular resistance, 6 minute walk distance, time to clinical worsening, SMURF1 inhibitor, echocardiography, patient reported outcomes

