1.2 Schema**Figure 1-1 Study Schema****1.3 Assessment Schedule**

The Assessment Schedule lists all of the assessments when they are performed. All data obtained from these assessments must be supported in the participant's source documentation. The "X" in the table denotes the assessments to be recorded in the clinical database or received electronically from a vendor. The "S" in the table denotes the assessments that are only in the participant's source documentation and do not need to be recorded in the clinical database.

Participants should be seen for all visits/assessments as outlined in the Assessment Schedule or as close to the designated day/time as possible. Missed or rescheduled visits should not lead to automatic discontinuation.

Participants who discontinue from study treatment are to complete the end of treatment visit as soon as possible, and attend the follow-up visits as indicated in the Assessment Schedule.

Participants who discontinue from study should be scheduled for a final evaluation visit if they agree, as soon as possible, at which time all of the assessments listed for the final visit will be performed. At this final visit, all dispensed investigational product should be reconciled, and the adverse events and concomitant medications not previously reported must be recorded on the CRF.

PRO measures must be completed before any assessments are performed at any given visit.

As per [Section 4.5](#), during a public health emergency as declared by local or regional authorities (i.e. pandemic, epidemic or natural disaster that limits or prevents on-site study visits), alternative methods of providing continuing care may be implemented by the Investigator as the situation dictates. If allowable by a local health authority, national and local regulations and depending on operational capabilities, phone calls, virtual contacts (e.g. tele consultation) or visits by site staff/ off-site healthcare professional(s) staff to the participant's home, can replace certain protocol assessments, for the duration of the disruption until it is safe for the participant to visit the site again. If the Investigator delegates tasks to an off-site healthcare professional, the Investigator must ensure the individual(s) is/are qualified and appropriately trained to perform assigned duties. The Investigator must oversee their conduct and remain responsible for the evaluation of the data collected.

Table 1-2 Assessment Schedule

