4.1 Overall design

Please refer to [Section 1.2 Schema](#) for study design figure.

This is a non-randomized, open-label extension study over 52 weeks with LTP001 without a control treatment arm. Participants will be presented the opportunity to consider the extension study at the End of Treatment (EOT) visit (Week 25) of the parent study CLTP001A12201. The investigator will assess if the participant will continue by verifying that the participant has completed the parent study as planned. Moreover, at the EOT the investigator will determine the eligibility for the extension study (i.e. that none of the treatment discontinuation criteria were met and that the assessments at the EOT of the parent efficacy study were completed according to the parent protocol). The patient may directly continue into the extension study. If the patient does not directly continue in the extension study, the time between the end of treatment assessments in the parent study and the enrollment in the extension study i.e. during the transition period should be kept to a minimum (it should not exceed 14 days).

Participants who are eligible and want to participate in the extension study will need to have signed an informed consent in order to receive the extension study treatment. In case of a direct transition into the extension study after the end of treatment visit in the parent study, as not all assessment results will be available (e.g. the central lab assessments) at the same day the investigator will re-assess/reconfirm the eligibility as soon as outstanding results are received.

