The safety and efficacy of LTP001 will be checked at the following visits: Weeks 5, 13, 26, 39 and 52, as specified in the Assessment Schedule. Safety and tolerability assessments will take place at each visit. RHC will be performed at week 26, 6MWT and echocardiography will be assessed at Weeks 26 and 52. PAH-SYMPACT and emPHasis-10 will be collected for 7 days intervals with the seventh day of collection occurring within the allotted visit window for all Treatment visits (Weeks 5, 13, 26, 39 and 52). Participants will have safety follow-up phone calls at Weeks 9 and 17, and may be invited for safety assessment at site if deemed necessary. The PI may exercise their discretion in which safety assessments are required at these optional safety follow-up visits. Following the end of treatment period, participants will have one safety follow-up phone call approximately 30 days after the end of treatment visit at Week 52. The duration of the extension study is currently restricted to 52 weeks, but the study may be prolonged (via an amendment to the protocol) if the LTP001 development program in PAH continues and the benefit/risk assessment remains favorable for the patient population studied. The safety and efficacy profile of LTP001 that is observed in this extension study as well as the parent study, CLTP001A12201, will determine continuation of the extension study.

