7.1 Discontinuation of study treatment

The investigator must also contact the IRT to register the participant's discontinuation from study treatment.

Discontinuation of study treatment for a participant occurs when study treatment is permanently stopped for any reason (prior to the planned completion of study drug administration, if any) and can be initiated by either the participant or the investigator.

The investigator must discontinue study treatment for a given participant if he/she believes that continuation would negatively impact the participant's well-being.

Discontinuation from study treatment is required under the following circumstances:

- Participant decision
- Pregnancy (if the participant decided to terminate the pregnancy, treatment with LTP001 may be resumed after the abortion procedure if desired by the participant and agreed by the investigator and the Novartis medical monitor).
- Any situation in which continued study participation might result in a safety risk to the participant
- Development of heart failure symptoms consistent with pulmonary hypertension WHO Functional Class IV (symptoms at rest; severe symptoms at exercise)
- If organ transplantation becomes necessary during the study treatment
- Atrial septostomy required due to deterioration of PAH
- Deterioration of PAH suggesting ineffectiveness of LTP001 as per the judgement of the investigator
- Adverse event that is graded severe or serious by the investigator and considered study drug related. If the investigator believes it is beneficial for the participant to stay on study drug (e. g. signs of PAH-improvement and adverse event appears well manageable) and the participant wishes to stay on study drug the investigator shall contact the Novartis medical monitor for further discussion.
- If a liver or renal event occurs, follow guidelines outlined in [Section 10.5](#) (Appendix 5) and [Section 10.6](#) (Appendix 6) regarding discontinuation of study treatment.

If discontinuation from study treatment occurs due to participant's decision, the investigator should make a reasonable effort to understand the primary reason for the participant's discontinuation from study treatment and record this information. In those instances where study drug discontinuation criteria were waived as per the exceptions defined above the decision made as well as the rationale for it needs to be documented in writing in the Trial Master File.

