8.3.4 Appropriateness of efficacy assessments

- The right heart catheterization allows an estimation of the progression of PAH by measuring the right heart and pulmonary arterial pressures as well as cardiac function. RHC is commonly employed in studies with PAH as a sensitive functional assessment to assess disease progression. In the scope of the current study it allows the detection of improvement within a small study population.
- Echocardiography is a commonly used technique to measure cardiac structure and functional parameters, is non-invasive and such allows more frequent monitoring without procedural risks.
- The 6MWT is a well standardized and simple test to assess physical performance.

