8.4 Safety assessments

Safety assessments are specified below with the Assessment Schedule detailing when each assessment is to be performed.

For details on AE collection and reporting, refer to AE section ([Section 8.6.1](#)).

As per [Section 4.5](#), during a public health emergency as declared by local or regional authorities (i.e. pandemic, epidemic or natural disaster, that limits or prevents on-site study visits), regular phone or virtual calls can occur (every 12 weeks or more frequently if needed) for safety monitoring and discussion of the participant's health status until it is safe for the participant to visit the site again.

Table 8-1 Safety Assessments

Assessment	Specification
Physical examination	
A complete physical examination will include the examination of general appearance, skin, neck (including thyroid), eyes, ears, nose, throat, lungs, heart, abdomen, back, lymph nodes, extremities, vascular, and neurological. If indicated based on medical history and/or symptoms, rectal, external genitalia, breast, and pelvic exams will be performed.
 
Information for all physical examinations must be included in the source documentation at the study site. Clinically relevant findings that are present prior to signing informed consent must be recorded on the appropriate CRF that captures medical history. Significant findings made after signing informed consent which meet the definition of an Adverse Event must be recorded as an adverse event.

Vital signs	
Vital signs will include the collection of otic or oral body temperature (recorded in °C), blood pressure (BP) and pulse measurements.
 
After the participant has been sitting for 3 minutes, with back supported and both feet placed on the floor, systolic and diastolic BP will be measured using an automated validated device, e.g. OMRON with an appropriately sized cuff. In case the cuff sizes available are not large enough for the participant's arm circumference, a sphygmomanometer with an appropriately sized cuff may be used.

Weight	Body weight (to the nearest 0.1 kilogram (kg) in indoor clothing, but without shoes) will be measured as specified in Table 1-1 .

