Descriptive statistics (N, mean, SD, CV% mean, geometric mean, CV% geometric mean, median, min, and max) summarizing RHC parameters and their changes from baseline will be summarized by visit/time for treatment group assigned in the parent study and overall.

Panels of individual spaghetti plots over time/visit for treatment group assigned in the parent study and overall for each RHC parameter will be provided.

All RHC parameters will be listed by participant, and visit and if ranges are available, abnormalities will be flagged.

Echocardiography/RVF

The echocardiography is performed to assess the impact of study drug on right heart structure and function. All echocardiography images will be centrally read by an imaging vendor. The measurement is taken at baseline and at visit on Day 176 and 358.

The assessed echocardiography parameters include:

- Tricuspid annular plane systolic excursion (TAPSE)
- Tricuspid annular systolic velocity (TASV)
- Peak velocity of excursion (RV S')

- Fractional area change (FAC)

Descriptive statistics (N, mean, SD, CV% mean, geometric mean, CV% geometric mean, median, min, and max) summarizing echocardiography parameters and their changes from baseline will be summarized by visit/time for treatment group assigned in the parent study and overall.

Panels of individual spaghetti plots over time/visit for treatment group assigned in the parent study and overall for each echocardiography parameter will be provided.

All echocardiography parameters will be listed by participant, and visit and if ranges are available, abnormalities will be flagged.

Time to clinical worsening (TTCW)

TTCW will be defined as time to any of the following events

- Death
- Hospital stay (≥ 24 h) due to worsening of PAH. Worsening of PAH is defined by the following right heart failure related signs and symptoms: syncope or near syncope, cyanosis, increase of breathlessness, clinically relevant deterioration of exercise capacity, decrease of oxygen saturation, increased peripheral edema, hepatomegaly, and ascites
- Worsening of PAH resulting in need for lung transplantation or balloon atrial septostomy
- Initiation of parenteral prostanoid therapy, chronic oxygen therapy, or any other PAH-specific therapies or need for increase of diuretics for more than 4 weeks due to worsening of PAH
- Disease progression (switch in modified New York Heart Association/WHO FC by at least one grade)

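### Functional class change counts as clinical worsening, but no functional class assessment is planned, so isolated worsening below Class IV may go uncounted

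*SAP*

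**What the plan says.** TTCW is a secondary endpoint. Among its components, SAP 2.6.1.1 lists "Disease progression (switch in modified New York Heart Association/WHO FC by at least one grade". The same component appears in SAP Table 1-1 and in Protocol Tables 1-1 and 3-1. None of these places gives a data source, a reference grade, a visit or a dating rule for it.

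Protocol Section 1.3 introduces the schedule with "The Assessment Schedule lists all of the assessments when they are performed". The legible rows of Table 1-2 include no functional class item. Protocol Section 8.3 describes NT-proBNP, echocardiography, right heart catheterisation and the 6-minute walk test (6MWT) with Borg score. Section 8.4 covers safety tests and Section 8.5 the two PRO questionnaires. Functional class is in none of them.

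Apart from the endpoint definition, functional class appears in the protocol only in Section 7.1, where a required reason to stop treatment is "Development of heart failure symptoms consistent with pulmonary hypertension WHO Functional Class IV".

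**The concern.** An endpoint component that nobody is scheduled to measure is recorded only when something else brings it to notice. For most TTCW components this does not matter, because the event itself generates a record. Functional class is different: it is a grade that someone must assign, and a change needs two grades, one of them at baseline.

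The loss would also leave no trace. Under SAP 2.6.1.1 a participant with no recorded event is censored when the time at risk ends. SAP 2.6.4 imputes nothing unless a rule is given, and none is given here. A participant who was never graded is therefore handled in the same way as one who was graded and stayed stable. The Kaplan-Meier curve would tend to look too favourable. The lower count could also affect whether survival models are fitted at all, because the SAP makes that depend on there being enough events and sets no threshold.

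**Working it through.** **Step 1. Planned source for each TTCW component**

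| Component | Planned source in the protocol |
|---|---|
| Death; hospital stay for PAH worsening | AE and SAE reporting, Section 8.6 |
| Need for lung transplantation or atrial septostomy | Section 7.1 discontinuation criteria; procedures recorded under 6.8.1 |
| New PAH therapy, chronic oxygen, sustained diuretic increase | Concomitant therapy records, Section 6.8.1 |
| Fall in 6MWD of 15% or more | Scheduled test: "6MWT and echocardiography will be assessed at Weeks 26 and 52" |
| One-grade functional class change | No scheduled grade; only Class IV symptoms would surface, through Section 7.1 |

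The nearest scheduled procedure is the physical examination. Table 1-2 marks it as source-only, and Table 8-1 says "Information for all physical examinations must be included in the source documentation at the study site". Its listed content is by body system, with no functional class grading. A site that did grade functional class there would not be required to enter it in the database.

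**Step 2. Which changes are exposed**

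Progression to Class IV should surface through Section 7.1. A change that accompanies hospitalisation, new therapy or a 6MWD fall is counted through that other component. What remains is functional-class-only worsening below Class IV, such as I to II or II to III.

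**Step 3. Illustrative size**

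The plan has no figure to reproduce: Protocol 9.9 and SAP Section 3 are both marked not applicable. The only document inputs are N of about 40 ("A total of approximately 40 participants are planned to complete the parent study CLTP001A12201") and the 80% interval for the hazard ratio in SAP 2.6.1.1. Everything else is assumed:

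- p, true proportion with a TTCW event: 10% to 30%
- f, share of those events that are functional-class-only: 10% to 40%
- m, share of those not recorded: 25% to 100%

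Formulas: lost = N × p × f × m; counted, d = N × p × (1 − f × m). With equal groups, the 80% limits for the hazard ratio are the estimate multiplied and divided by exp(1.2816 × √(4/d)).

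| Case | p, f, m | True events | Lost | Counted | Proportion | 80% CI factor |
|---|---|---|---|---|---|---|
| Lowest | 10%, 10%, 25% | 4.0 | 0.1 | 3.9 | 10% to 9.8% | 3.60 to 3.66 |
| Middle | 20%, 25%, 50% | 8.0 | 1.0 | 7.0 | 20% to 17.5% | 2.47 to 2.63 |
| 20% rate, worst | 20%, 40%, 100% | 8.0 | 3.2 | 4.8 | 20% to 12% | 2.47 to 3.22 |
| Largest loss | 30%, 40%, 100% | 12.0 | 4.8 | 7.2 | 30% to 18% | 2.10 to 2.60 |

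For the middle case: 40 × 0.20 × 0.25 × 0.50 = 1.0 lost, leaving 7.0; the proportion is 7.0/40 = 17.5%, and the factor is exp(1.2816 × √(4/7)) = 2.63. The proportions ignore censoring.

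**The case against.** The strongest reply is that a missing row does not prove missing data. The schedule is not strictly exhaustive: Protocol 5.3.1.1 collects changes in smoking status on the CRF without a row for it. The CRF is not among the documents, and parts of the protocol are redacted, so a functional class field or a hidden row cannot be ruled out. AE questioning at every visit and investigator review of the PROs give further chances to notice deterioration. The consequence is also limited: TTCW is one of several secondary endpoints in a study described as "This is a non-randomized, open-label extension study over 52 weeks with LTP001 without a control treatment arm", whose primary aim is safety.

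Part of this stands. A hidden row is possible, though unlikely, since the component itself is unredacted wherever it appears and no legible text in Section 8 describes it. An AE of breathlessness carries a severity grade, not a functional class, so it does not establish a one-grade change. If a CRF field does exist, the protocol and SAP still need to say so.

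Three stronger readings are tempting, and the documents do not support them:

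- A reader might infer that the component is caught only by chance. Class IV and accompanying worsening have other routes, as Step 2 shows.
- A reader might infer from the word for a change of grade that an improvement counts as an event. The component is headed as disease progression and sits under clinical worsening, so the direction is implied. An explicit programming rule would still help.
- A reader might infer that uneven recording biases the comparison of parent treatment groups. Protocol 1.1 plans no unblinding of parent treatment, so there is no stated reason for recording to differ by group. The expected harm there is fewer events and a wider interval.

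**Conclusion.** The point holds in a limited form. The plan uses functional class as an event criterion but shows no planned grade at baseline or during the extension. Functional-class-only worsening below Class IV can therefore be missed and treated as event-free, and the expected direction is under-counting of clinical worsening.

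The loss of 0.1 to 4.8 events is an illustration, not an estimate. The event rate, the functional-class-only share and the unrecorded share are all assumed, and no figure in the plan depends on them. The calculation counts only events never recorded; an event dated late still counts. The primary safety objective is not affected. The gap is worth closing because TTCW will have few events and each one matters to its summary.

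**What to change.** **Protocol.** Add WHO functional class to Table 1-2 and Section 8.3, recorded in the database, at the existing visits at Weeks 5, 13, 26, 39 and 52. Take the baseline grade from the parent study's Week 25 visit if it was recorded there, which these documents do not show. Otherwise grade before the first extension dose. Because Table 1-2 lets most assessments be done off-site, state who assigns the grade.

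**SAP 2.6.1.1.** State which of the two baselines in SAP 2.1.1 applies to this component, that only worsening by at least one grade counts, and how the event is dated.

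**If the item cannot be added.** Remove the component from TTCW and record this in SAP Section 4, which currently reports no changes.

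**Cost.** An amendment, one CRF field and one extra item per visit. Visits already completed cannot be back-filled, so detection would differ before and after the change, and the SAP should note this when TTCW is reported.

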9.4 Secondary endpoint(s)/estimand(s) analysis

9.4.1 Efficacy and/or pharmacodynamic endpoint(s)

Change from baseline for efficacy endpoints including the right heart catheterization (RHC) parameters, 6-Minute Walk Distance (6MWD), and N-terminal fragment of the prohormone B-type natriuretic peptide (NT-proBNP) will be descriptively summarized by visit/time for treatment group (treatment received in the parent study), and overall. The baseline measurement for the extension will be the baseline measurement taken during the parent study CLTP001A12201. Graphs (e.g., spaghetti plot) will be provided to show individual time courses of parameters for the extension study together with the parent study.

Additionally, changes from baseline for efficacy endpoints will be descriptively summarized by visit/time for treatment group (treatment received in the parent study), and overall using a different baseline strategy: participants receiving LTP001 in the parent study will use the baseline of parent study as the baseline; participants switching from placebo in parent study to LTP001 in extension study will use the baseline of extension study as the baseline.

Time to clinical worsening will be analyzed using survival analysis (i.e., Kaplan-Meier) and the corresponding 80% confidence interval will be computed using the appropriate method.

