- Significant drop in 6MWD (15% from baseline or more) due to PAH-worsening

Time to clinical worsening will be analyzed using survival models (i.e., Kaplan-Meier, cox regression) if adequate number of events occur during the study to characterize the survival curve. Participants without the event will be considered as censored at the end of the time at risk. The hazard ratio between the treatment group assigned in the parent study and the corresponding 80% confidence intervals will be computed using the appropriate method. If there is no adequate number of events, the number (and percentage) of participants with clinical worsening will be summarized by treatment group assigned in the parent study and overall.

NT-proBNP

Descriptive statistics (N, mean, SD, CV% mean, geometric mean, CV% geometric mean, median, min, and max) summarizing N-terminal fragment of the prohormone B-type natriuretic peptide , NT-proBNP (visits on Day 29, 85, 176, 267 and 358) and its changes from baseline will be summarized by visit/time for treatment group assigned in the parent study and overall.

Spaghetti plot over time/visit will be provided. And the endpoint will be listed by participant, and visit and if ranges are available, abnormalities will be flagged.

Change from baseline for efficacy endpoints will be descriptively summarized by visit/time for treatment group assigned in the parent study, and overall. The baseline measurement for the extension will be the baseline measurement taken during the parent study CLTP001A12201. Graphs (e.g., spaghetti plot) will be provided to show individual time courses of parameters for the extension study together with the parent study.

Additionally, changes from baseline for efficacy endpoints will be descriptively summarized by visit/time for treatment group assigned in the parent study, and overall using a different baseline strategy: participants receiving LTP001 in the parent study will use the baseline of parent study as the baseline; participants switching from placebo in parent study to LTP001 in extension study will use the baseline of extension study as the baseline.

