2.6.2 Statistical hypothesis, model, and method of analysis

Most analyses will be conducted descriptively using summary statistics and visualization of the time course for each endpoints using graphical presentations (e.g. spaghetti plots). statistical models may be used when data allows for TTCW. Detailed method of analyses are specified under each endpoint in [Section 2.6.1.1](#).

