2.14 Interim analysis

Not applicable.

3 Sample size calculation

Not applicable.

4 Change to protocol specified analyses

Not applicable.

5 Appendix

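### The SAP makes Kaplan-Meier for time to clinical worsening depend on an undefined event count, with a crude percentage and no interval as fallback, where the protocol sets no condition

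*SAP*

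**What the plan says.** Protocol 9.4.1: "Time to clinical worsening will be analyzed using survival analysis (i.e., Kaplan-Meier) and the corresponding 80% confidence interval will be computed". No minimum number of events is attached.

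SAP 2.6.1.1 plans "survival models (i.e., Kaplan-Meier, cox regression) if adequate number of events occur during the study to characterize the survival curve". One condition therefore governs both the curve and the regression model. Otherwise: "If there is no adequate number of events, the number (and percentage) of participants with clinical worsening will be summarized", by parent-study group and overall, with no interval.

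No threshold is given anywhere. SAP 2.6.2 says only that "statistical models may be used when data allows for TTCW", and SAP 5.4 (Statistical models) is marked not applicable.

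Two related details in SAP 2.6.1.1:

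- The interval, "the corresponding 80% confidence intervals will be computed using the appropriate method", is attached to the hazard ratio. Even when the condition is met, no interval is stated for the Kaplan-Meier curve.
- The censoring rule is "Participants without the event will be considered as censored at the end of the time at risk", but time at risk is not defined.

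SAP section 4, "Change to protocol specified analyses", reads not applicable.

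**The concern.** The protocol fixes the method in advance. The SAP lets it be chosen after the event count is known, on an unstated criterion, and does not declare the departure.

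An event minimum makes sense for a Cox model. A Kaplan-Meier curve can be estimated with any number of events, although its interval needs care when there are very few.

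The fallback also drops the time element from a time-to-event endpoint. Anyone whose follow-up ends early stays in the denominator as event-free for the whole year. Unequal follow-up is foreseeable: protocol 7.6 lets the sponsor stop the study at any time, including for inadequate efficacy, and protocol 4.1 ties continuation to results from this study and its parent. With about 40 participants (protocol section 5), few events is a realistic outcome, so the fallback could well be the analysis reported.

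**Working it through.** The documents give no event rate, dropout rate or sample-size figure for TTCW (protocol 9.9 is not applicable), so there is no plan figure to reproduce. Taken from the documents: about 40 participants, 52 weeks of treatment, 80% intervals, end of treatment at Day 358 ±10. Event risk and censoring are assumptions, shown as ranges.

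**1. Crude percentage against 52-week risk.** Let r be the true 52-week risk and d the chance of being censored within 52 weeks in the absence of an event. Both times are exponential, with h = −ln(1−r) and c = −ln(1−d) per year.

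- Expected crude proportion = h/(h+c) × (1 − e^−(h+c)).
- Example, r = 0.10 and d = 0.20: h = 0.1054, c = 0.2231, so 0.1054/0.3285 × (1 − e^−0.3285) = 0.3208 × 0.2800 = 0.0898.
- Early stop, follow-up uniform over 13 to 52 weeks (0.25 to 1 year): 1 − (e^−0.25h − e^−h)/(0.75h). For r = 0.10: 1 − (0.9740 − 0.9000)/0.0790 = 0.0635.

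| True 52-week risk | Complete follow-up | 20% censored | 30% censored | Early stop |
|---|---|---|---|---|
| 5% | 5.00 | 4.49 | 4.21 | 3.15 |
| 10% | 10.00 | 8.98 | 8.44 | 6.35 |
| 20% | 20.00 | 18.00 | 16.93 | 12.92 |

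The rows most relevant to the fallback are 5% and 10%, which mean 2 and 4 events in 40 with full follow-up. There the gap is 0.51 to 1.56 points with 20 to 30% censoring, and 1.85 to 3.65 points in an early stop (37% and 36% relative).

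**2. Direction.** In 30,000 simulated trials of 40 participants the crude percentage never exceeded the Kaplan-Meier figure, and mean Kaplan-Meier estimates were within about 0.2 points of the true risk. Worked case: 4 events in 40, with 10 participants censored before the first event and none between events. Crude is 4/40 = 10.0%. Kaplan-Meier is 1 − (29/30 × 28/29 × 27/28 × 26/27) = 4/30 = 13.3%.

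**3. Why Cox differs.** With equal groups, the 80% interval for a hazard ratio extends by a factor of e^(1.2816 × √(4/events)) either side. That is 3.60 with 4 events and 2.47 with 8.

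**4. Intervals with few events.**

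- 3 of 40, full follow-up: 7.5% ± 1.2816 × √(0.075 × 0.925/40), or 2.2 to 12.8%. The exact 80% interval is 2.8 to 15.9%.
- 1 of 20 (an assumed group size): the plain Greenwood interval is −1.2 to 11.2%; the exact interval is 0.5 to 18.1%.
- 0 of 20: the Greenwood standard error is zero; the exact upper limit is 1 − 0.1^(1/20) = 10.9%.

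**5. Visit timing.** The 6-minute walk is scheduled only at Weeks 26 and 52. On actual days, a participant finishing event-free on Day 350 leaves the risk set before another's walk-distance drop is found on Day 362. I simulated 4,000 trials of 40 with no dropout, a true risk of 10%, and end of treatment uniform over Days 348 to 368. Read at Day 364, Kaplan-Meier averaged 14.4% when all events were found at that visit and 12.5% when half were. Read at Day 368 on actual days, it averaged 30.1% and 21.0%. With end-of-treatment events and censoring both placed at Day 358, it returned to 10.0%.

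**The case against.** **The bias is conditional.** A reader might infer that the crude percentage always understates worsening. The documents do not support that. With complete 52-week follow-up the two figures agree, and at 5 to 10% risk with modest dropout the gap is small beside the uncertainty from 40 participants. This objection stands and limits the size of the point.

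**It need not favour LTP001.** A reader might infer that the fallback flatters the drug. There is no control arm, both parent-study groups receive LTP001 in the extension, and similar censoring would lower both percentages. Only a comparison with an outside rate would be flattered, and none is planned. This stands.

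**Stopping treatment is not automatically loss of follow-up.** Protocol 7.1 asks for at least adverse events and new or concomitant treatments after discontinuation, by telephone if needed. Deaths, hospital stays and new therapies may still be captured, though how long this lasts is not fully clear. This stands in part; it does not cover sponsor termination.

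**Kaplan-Meier can do worse if specified carelessly.** Working steps 4 and 5 confirm this: plain intervals break down with 0 or 1 events, and actual-day timing biases the Week 52 estimate upward. It is a reason to specify the method, not to drop it.

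**TTCW is one of several secondary endpoints** in an uncontrolled extension without hypothesis tests. That limits the consequences but does not explain an undeclared departure from the protocol.

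**Conclusion.** The point holds. The SAP replaces an unconditional protocol commitment with a method chosen on an undefined event count. Its fallback carries neither an interval nor any allowance for follow-up time, and section 4 does not list the change. These facts do not depend on dropout.

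The numerical harm does depend on it. It is nil with complete follow-up, about 0.5 to 1.6 points at 5 to 10% risk with 20 to 30% early censoring, and about 2 to 4 points (somewhat over a third, relative) if an early stop spreads follow-up uniformly over 13 to 52 weeks. These figures rest on assumed risks, exponential times and censoring unrelated to prognosis. Kaplan-Meier also relies on that last assumption, so it does not remove every bias. The change is worth making, but the primary safety analysis is not affected.

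**What to change.** In SAP 2.6.1.1, with 2.6.2 aligned:

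- Always report the Kaplan-Meier cumulative proportion with clinical worsening, with numbers at risk and an 80% interval, by parent-study group and overall, beside the count and percentage.
- Name an interval method that works with few events: for example log-log, with an exact binomial-type interval when a group has 0 or 1 events.
- Define time at risk. Assign events found at the Week 26 and Week 52 visits, and censoring at those visits, to the nominal visit day. Reading an actual-day curve at the end of the window is not a substitute unless event-free completers are also carried to that day (working step 5).
- Keep an event condition for the Cox hazard ratio only, and state the number.
- List any remaining departure from protocol 9.4.1 in section 4.

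The cost is SAP wording and modest programming on data already collected. The downside is wide intervals when events are few, which correctly shows how little such data can say.
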